#### **9.4 Visit 4: 14-Day Post-OCR**

Visit 4 will take place 14 ± 3 days after Visit 3, OCR Evaluation only for subjects who required a touch-up injection in Visit 3 in order to achieve OCR.

The following procedures will be performed:

1. Subject completes the SHS questionnaire.
2. Subject completes the HM questionnaire.
3. Subject completes a self-reported GAIS (S-GAIS).
4. PI completes the GAIS form (PI-GAIS).
5. PI rates the subject on the OCSS and POLSS at rest.
6. Subject undergoes standardized digital photography and video of full face in accordance with the site's SOP (described in Appendix I);
7. A report of occurrence of any AEs and changes in concomitant medications is obtained from the subject.

#### **9.5 Post-Visit Evaluations**

Photographs of subjects taken at Visit 1, Screening Assessments and at Visit 4, 14-Day Post-OCR will be used to assess alterations in the projected first impression (see Section 10.1.1 for further details).

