**Study Duration**

Subjects will be followed for 14 days after a treatment that has produced Optimal Cosmetic Results.

---

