## 6 STUDY DESIGN

This is an open-label, post-market study to assess the impact of lip rejuvenation with Restylane® Silk on the projected first impression and the self-perception of mood.

20 subjects, at least 21 years of age, who display mild to severe oral commissures or none to severe perioral lines, as judged by the Principal Investigator (PI) utilizing the Oral Commissure Severity Scale (OCSS, Appendix G) or the Perioral Lines Severity Scale (POLSS, Appendix H), will be enrolled.

The study is composed of up to 4 patient visits and a post-visit evaluation of patients' photographs by blinded evaluators. A schematic of the study design is presented in Appendix A.

All subjects who meet the specified criteria, listed in Section 7, will complete the Subjective Happiness Scale (SHS, Appendix B) and the Happiness Measures questionnaire (HM, Appendix C) prior to receiving any treatments. The PI also records the severity of subjects' oral commissures and/or the perioral lines using the OCSS and/or the POLSS respectively. Furthermore, all subjects undergo photo- and videography, as described in Appendix I, prior to treatment.

Subjects will then be injected with Restylane® Silk with a volume sufficient to achieve Optimal Cosmetic Results (OCR), per treating investigator's discretion but not to exceed a total of 4ml (4 syringes). Subjects will be assessed 14 ± 3 days after injection for achieving the OCR. If OCR has not been reached, as judged by the PI, a second, 'touch-up,' injection of Restylane® Silk will be performed.

The final evaluation of subjects will take place 14 ± 3 days after achieving OCR. Hence, this would be 14 ± 3 days after the first injection for those who achieved OCR with one treatment but 28 ± 3 days after the first injection for those who required a 'touch-up' injection. Subjects will complete the SHS and HM questionnaires as well as self-report any aesthetic alterations experienced using the Global Aesthetic Improvement Scale (GAIS, Appendix D). They will also undergo photo- and videography, as described in Appendix I. Furthermore, the PI will rate the subjects on the GAIS (Appendix E) as well as on the OCSS and the POLSS.

Photographs taken at pre-treatment and 14-Day Post-OCR will be randomly divided into 4 binders, for a total of 10 photographs per binder. Each binder will be evaluated at least by 50 blinded evaluators using the First Impressions Questionnaire (FIQ, Appendix F) to rate each photograph.

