## 9.3 Visit 3: OCR Evaluation

The following procedures will be performed 14 ± 3 days after Visit 2, Treatment:

1. PI assesses the subject for achieving the OCR.
2. At PI's discretion, subject may receive a touch-up treatment in order to achieve OCR (not to exceed a total dose of 4 ml of Restylane® Silk).
3. A report of any AEs and changes in concomitant medications is obtained from the subject.

Subjects who require a touch-up injection will be instructed to return for the forth and final visit in 14 ± 3 days. For those who have achieved OCR, and hence do not require a touch-up injection, the following procedures will be performed:

1. Subject completes the SHS questionnaire.

2. Subject completes the HM questionnaire.
3. Subject completes a self-reported GAIS (S-GAIS).
4. PI completes the GAIS form (PI-GAIS).
5. PI rates the subject on the OCSS and POLSS at rest.
6. Subject undergoes standardized digital photography and video of full face in accordance with the site's SOP (described in Appendix I);

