#### **10.1.1 Assessment of First Impressions**

Upon completion of the study, a minimum of 200 blinded evaluators will assess one of four binders, for a minimum of 50 blinded evaluators per binder, each comprised of 10 photographs selected randomly from Visit 1 (baseline) or Visit 4 (14-Day Post-OCR) for each subject. The

FIQ will be completed by each evaluator for each photo (see Appendix F). Each photograph will be graded based on a 10-point numerical rating scale for each of the 8 categories listed below:

- *Social skills*: Social desirability, temperament, positive mood, getting along with others, friendliness
- *Academic performance*: Intelligence, educational skills
- *Dating success*: Frequently invited, lack of dating anxiety, thought of positively after dating encounter
- *Occupational success*: Job performance, competence, motivation for success, suitability as potential employee
- *Attractiveness*: Pleasing appearance
- *Financial success*: Has achieved or is a member of an elevated socioeconomic status
- *Relationship success*: Willingness to compromise put the relationship health before their own desires or gain, Ability to maintain long term friendships
- *Athletic skills*: Ability to excel at athletic events, including individual and team sports

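### Eight subsections take the post-treatment photographs and scores from Visit 4, which only touch-up subjects attend

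*Combined protocol and SAP*

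**What the plan says.** All references are to the combined protocol and SAP.

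**Which visit supplies the post-treatment record.** Section 9.5: "Photographs of subjects taken at Visit 1, Screening Assessments and at Visit 4, 14-Day Post-OCR will be used" for the first-impression assessment. Section 10.1.1 has the binder photographs "selected randomly from Visit 1 (baseline) or Visit 4 (14-Day Post-OCR) for each subject". Sections 10.1.2 (Subjective Happiness Scale, SHS), 10.1.3 (Happiness Measures, HM), 10.2.1 (S-GAIS), 10.2.2 (PI-GAIS), 10.2.3 (OCSS) and 10.2.4 (POLSS) also name Visit 4. None of the eight mentions Visit 3.

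**Who attends which visit.** Section 9.4 holds Visit 4 "only for subjects who required a touch-up injection in Visit 3 in order to achieve OCR", and Appendix A footnote d agrees. For everyone else, section 9.3 says: "For those who have achieved OCR, and hence do not require a touch-up injection, the following procedures will be performed". The list that follows contains the same questionnaires, ratings and photographs, and footnote c agrees.

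**Timing.** Section 6 sets the final evaluation by route: "this would be 14 ± 3 days after the first injection for those who achieved OCR with one treatment", and 28 ± 3 days for those who needed a touch-up. The Study Duration entry in the synopsis is also tied to the successful treatment and not to a visit number: "Subjects will be followed for 14 days after a treatment that has produced Optimal Cosmetic Results".

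**Who is analysed.** Section 12.2 puts all enrolled and treated subjects into the analyses. Section 6 has the photographs "randomly divided into 4 binders, for a total of 10 photographs per binder".

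**The concern.** The eight subsections are the only text that ties each measure to a numbered visit, and they cover FIQ, SHS, HM, S-GAIS, PI-GAIS, OCSS and POLSS: every primary and secondary endpoint. A programmer who extracts by visit number would find no post-treatment record for any subject who reached OCR with one treatment. The subjects left would be those who had not reached OCR after the first treatment, so the analysed group would be selected on initial response as well as being smaller. A colleague who reads the same plan together with section 6 would keep both routes. The data set should not depend on which of these two readers prepares it.

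Two related slips sit in the same text.

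- Sections 10.2.3 and 10.2.4 give the OCSS and POLSS baseline as Visit 1 but call that visit Treatment. Treatment is Visit 2, and section 9.2 and Appendix A schedule these ratings there. Neither scale is a scheduled Visit 1 outcome, although section 6 uses one or the other to judge eligibility, which section 9.1 confirms at Visit 1.
- Section 9.3 says that, at the PI's discretion, a "subject may receive a touch-up treatment in order to achieve OCR", while section 6 makes the touch-up automatic when OCR has not been reached. Under section 9.3 a subject could have neither OCR at Visit 3 nor a touch-up, and would then have no scheduled final assessment.

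**Working it through.** **Step 1: count the affected subsections.** Photographs: 9.5 and 10.1.1 (2). Scores: 10.1.2, 10.1.3, 10.2.1, 10.2.2, 10.2.3 and 10.2.4 (6). Total 2 + 6 = 8.

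**Step 2: reproduce the plan's photograph total.** Section 6 gives 4 binders × 10 photographs = 40. With 20 subjects and two time points, 20 × 2 = 40. The design therefore works only if all 20 subjects supply a post-treatment photograph. It also implies one photograph per subject per time point; Appendix I lists five poses, and the plan does not say which one is used.

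**Step 3: apply the Visit 4 rule as written.** Let k be the number of subjects who receive a touch-up, and assume full attendance. The documents give no value for k, so it can lie anywhere from 0 to 20.

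- Photographs available: 20 baseline + k post-treatment = 20 + k.
- Before-after pairs for FIQ, SHS and HM: k of 20.
- Subjects without a post-treatment value: 20 − k.
- Standard error of the mean within-subject change, relative to all 20 subjects at the same SD of change: (SD/√k) ÷ (SD/√20) = √(20/k).

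| k (assumed) | Photographs, 20 + k | Pairs | Subjects lost | √(20/k) |
|---|---|---|---|---|
| 0 | 20 | 0 | 20 | not defined |
| 5 | 25 | 5 | 15 | √4.00 = 2.00 |
| 10 | 30 | 10 | 10 | √2.00 = 1.41 |
| 15 | 35 | 15 | 5 | √1.33 = 1.15 |
| 20 | 40 | 20 | 0 | 1.00 |

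The planned 40 is reached only if every subject needs a touch-up.

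**Step 4: apply the section 6 rule.** If the post-treatment record is taken from Visit 3 for one-treatment subjects and from Visit 4 for touch-up subjects, the count is 20 + k + (20 − k) = 40 for any k. This agrees with the binder design and with section 12.2.

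**Step 5: check whether the time-point label settles it.** Sections 10.1 and 12.3 use only the label 14-Day Post-OCR, with no visit number. That label is also the title of Visit 4 in section 9.4 and of the Visit 4 column in Appendix A, which is set at Day 28 (±3). Section 6 places the final evaluation of one-treatment subjects at 14 ± 3 days. The label alone can therefore lead back to the visit that those subjects do not attend.

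**The case against.** The strongest reply is that the sections defining the endpoints do not contain the error. Sections 12.3.1, 12.3.2 and 10.1 refer to 14-Day Post-OCR without a visit number. Section 6 uses the same label as a time point for all subjects and spells out both routes; section 9.3 and footnotes c and d agree. On this view the defect is a stale visit number attached to a usable label. In a one-centre study of 20 subjects with manual data review, a shortfall from 40 photographs would be noticed when the binders were put together. The standard-error ratios describe a reading that the protocol itself contradicts, and the baseline label and the touch-up wording are separate matters.

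Much of this stands. The intent is recoverable, data collection covers both routes, the values of k are illustrative, and the two related slips are secondary. It does not remove the conflict. The label is also the name of Visit 4, eight subsections consistently attach that visit number, and section 10.1.1 applies it to each subject. The binder check would catch missing photographs, but it offers no such safeguard for the questionnaires and ratings.

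**Conclusion.** The inconsistency is real and should be corrected. As written, the selection rule in eight subsections excludes every one-treatment subject's post-treatment value from all three primary and four secondary endpoints, contrary to section 6, the Study Duration entry, section 12.2 and the 40-photograph design.

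The size of the loss cannot be fixed without a touch-up rate. It is 20 − k subjects under the literal reading, assuming full attendance and one photograph per subject per time point, and none if the text is read with section 6. Because the correct reading can be worked out from the rest of the protocol, this is a fault in the selection text and not in the data collected.

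**What to change.** 1. In sections 9.5, 10.1.1–10.1.3 and 10.2.1–10.2.4, replace the Visit 4 reference with one definition: *the 14-Day Post-OCR assessment (Visit 3 for subjects judged to have achieved OCR at Visit 3; Visit 4 for subjects who received a touch-up at Visit 3)*. Select records by that definition.
2. Report how many subjects contribute from Visit 3, how many from Visit 4, and how many have neither record.
3. Reconcile the touch-up wording in section 9.3 with section 6, since the possibility of a subject with neither record rests on that difference.
4. Reconcile the OCSS and POLSS baseline label in sections 10.2.3 and 10.2.4 with section 9.2 and Appendix A.

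The cost is wording in eight short subsections, reconciliation of the touch-up passages, and one count in the report. The visit schedule does not change. The edit counts any subject with neither OCR at Visit 3 nor a touch-up, but it does not supply the missing assessment.

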## **10 RESPONSE CRITERIA**

### **10.1 Primary Variable Assessments**

The primary assessment of this study is to determine if subjects who receive lip rejuvenation treatment with Restylane® Silk would project a more positive first impression as well as experience a more positive mood perception as compared to their baseline. The primary efficacy will be established by comparing the projected first impression of subjects at 14-Day Post-OCR with that of the baseline. The change in mood perception will be determined by comparing the SHS and HM results from 14-Day Post-OCR with those from the baseline.

#### **10.1.1 Assessment of First Impressions**

Upon completion of the study, a minimum of 200 blinded evaluators will assess one of four binders, for a minimum of 50 blinded evaluators per binder, each comprised of 10 photographs selected randomly from Visit 1 (baseline) or Visit 4 (14-Day Post-OCR) for each subject. The

FIQ will be completed by each evaluator for each photo (see Appendix F). Each photograph will be graded based on a 10-point numerical rating scale for each of the 8 categories listed below:

- *Social skills*: Social desirability, temperament, positive mood, getting along with others, friendliness
- *Academic performance*: Intelligence, educational skills
- *Dating success*: Frequently invited, lack of dating anxiety, thought of positively after dating encounter
- *Occupational success*: Job performance, competence, motivation for success, suitability as potential employee
- *Attractiveness*: Pleasing appearance
- *Financial success*: Has achieved or is a member of an elevated socioeconomic status
- *Relationship success*: Willingness to compromise put the relationship health before their own desires or gain, Ability to maintain long term friendships
- *Athletic skills*: Ability to excel at athletic events, including individual and team sports

### **10.1.2 Subjective Happiness Scale (SHS) Evaluation**

Changes in subjects' mood will be determined partially through the SHS questionnaire (Appendix B) completed by subjects at Visit 1, Screening Assessments (baseline) and at Visit 4, 14-Day Post-OCR.

### **10.1.3 The Happiness Measures (HM) Evaluation**

Changes in subjects' mood will be determined partially through the HM questionnaire (Appendix C) completed by subjects at Visit 1, Screening Assessments (baseline) and at Visit 4, 14-Day Post-OCR.

## **10.2 Secondary Variable Assessments**

The secondary variables evaluated in this study include changes in the overall aesthetic improvements, determined as described below.

### **10.2.1 Subject Global Aesthetic Improvement Scale (S-GAIS) Evaluation**

Changes in global aesthetics will be determined through subjects' self-assessments utilizing the GAIS (Appendix D) at Visit 4, 14-Day Post-OCR.

### **10.2.2 PI Global Aesthetic Improvement Scale (PI-GAIS) Evaluation**

Changes in global aesthetics will be determined partially by the PI's assessment of subjects at Visit 4, 14-Day Post-OCR utilizing the GAIS (Appendix E).

### **10.2.3 Oral Commissure Severity Scale (OCSS) Evaluation**

Aesthetic improvement will be determined by the PI's assessment of subjects at Visit 1, Treatment (baseline) and at Visit 4, 14-Day Post-OCR partially through utilizing the OCSS (Appendix G)

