## 9 STUDY PROCEDURES

### 9.1 Visit 1: Screening Assessments

The PI and/or designee is responsible for keeping a record of all subjects screened for entry into the study as well those who did not meet the criteria, as described in Section 7, and hence were excluded.

The following procedures will be performed:

1. The PI or designee evaluates and confirms that the subject fulfills all the inclusion/exclusion criteria, as described in Section 7.

2. A written informed consent, signed by the subject as well as by the investigator or designee, is obtained.
3. Demographic information and medical history are obtained.
4. List of concomitant medications is collected.
5. Vital signs (blood pressure and pulse rate) are measured.
6. If the subject is a female of child bearing potential, a urine collection for in-clinic pregnancy test will be conducted.
7. Subject completes the SHS questionnaire
8. Subject completes the HM questionnaire.
9. Subject undergoes standardized digital photography and video of full face in accordance with the site's SOP (described in Appendix I).

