#### 12.3.2 Secondary Endpoints

1. S-GAIS evaluation at 14-Day Post-OCR
2. PI-GAIS evaluation at 14-Day Post-OCR
3. OCSS evaluation at 14-Day Post-OCR
4. POLSS evaluation at 14-Day Post-OCR

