## Appendix I Standard Operating Protocol for Photo- and Videography

### Photography and Poses

- Use the grid feature on any of these viewers to ensure the Frankfort Plane (imaginary line from tragus to infraorbital rim) is parallel to the floor.
- Stand approximately 1.5 m from patient with the camera in a portrait position.
- Ensure the patient has a relaxed expression and that lips are closed and eyes are open for each photo.
- Give instructions like, “Slowly move your chin down” or “Slowly turn your nose to the left” to achieve the desired poses listed below
- Standard Poses (all at 1.5 m)
  1. Frontal  
Make sure the patient doesn’t have their chin high or low by checking the Frankfort Plane. For this view, the line on the viewfinder should extend from the right tragus, across both infraorbital rims and across the left tragus. This should be parallel to the floor.
  2. 45° Left  
For this view, the tip of the nose should line up with the edge of the cheek.
  3. Left Profile  
For this view, ensure the patient is not rotated to the left or right (hint: look at the eyebrows to see how much of the glabella you see).
  4. 45° Right  
For this view, the tip of the nose should line up with the edge of the cheek.
  5. Right Profile  
For this view, ensure the patient is not rotated to the left or right (hint: look at the eyebrows to see how much of the glabella you see).

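### OCSS and POLSS are graded live by a PI who knows the visit and also judges OCR: add a visit-masked reading of the existing photographs beside the live grades

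*Combined protocol and SAP*

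**What the plan says.** - **Design.** Section 6: "This is an open-label, post-market study to assess the impact of lip rejuvenation with Restylane® Silk". There is one group, and every enrolled subject is injected.
- **Baseline grade.** Section 9.2 has the PI grade both scales in person at Visit 2, before the injection.
- **Final grade.** Section 9.3 begins with "PI assesses the subject for achieving the OCR". For subjects who need no touch-up, the same visit then lists the questionnaires, the PI's GAIS and, after those, "PI rates the subject on the OCSS and POLSS at rest". Subjects who had a touch-up are graded by the PI at Visit 4 (Section 9.4).
- **Endpoints.** Section 10.2.3: "Aesthetic improvement will be determined by the PI's assessment of subjects", at a baseline that it labels Visit 1 and again at Visit 4. Section 10.2.4 says the same for POLSS. Section 12.3.2 lists both as secondary, for example "OCSS evaluation at 14-Day Post-OCR". No masking, second reader or photographic grading is specified for either scale.
- **Photographs.** Section 9.1: "Subject undergoes standardized digital photography and video of full face in accordance with the site's SOP". The same step appears at the final visit (9.3 or 9.4). Appendix I asks for five views at 1.5 m and instructs: "Ensure the patient has a relaxed expression and that lips are closed and eyes are open for each photo".
- **Masking elsewhere.** Sections 6 and 10.1.1 have blinded evaluators rate photographs, but only for the FIQ.
- **Analysis.** Section 12.4 gives descriptive statistics and a general two-sided 0.05 level. It names no test for OCSS or POLSS.

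**The concern.** The first grade is always given before treatment and the second always after it, by a rater who knows which is which. For subjects without a touch-up, the final severity grade is also listed after the PI's own decision that OCR has been reached and after the PI's GAIS. With no untreated subjects, a lenient reading on the second occasion has nothing to offset it and looks the same as a product effect.

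At stake is the secondary objective in Section 5, which is to evaluate aesthetic improvement and relate it to first impression and mood. All four secondary endpoints are unmasked. The two GAIS ratings ask for change from before treatment, so they cannot be given without knowing the visit. OCSS and POLSS grade a static appearance, so in principle they can be.

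**Working it through.** **The plan's own figure.** The only power statement is in Section 12.1 and concerns the total FIQ score: 20 subjects, SD 14, difference 2.5, α = 0.05, power about 8%. It reproduces for two independent sets of 20: 2.5 / (14 × √(2/20)) = 0.565, and Φ(0.565 − 1.96) = 0.081. It has no bearing on OCSS or POLSS, for which the plan states no figure.

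**Who knows what, and when.**

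| Step | Rater | Visit known? | Rater's prior judgement |
|---|---|---|---|
| Baseline (Visit 2) | PI, live | yes | none |
| Final, no touch-up (Visit 3) | PI, live | yes | OCR judged reached; PI-GAIS listed first |
| Final, after touch-up (Visit 4) | PI, live | yes | touch-up judged necessary at Visit 3; PI-GAIS listed first |

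The risk and its direction follow from this table. Its size does not.

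**What a shift would do (assumed counts).**

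- If 4 of 20 subjects are graded one step too favourably, the mean change is inflated by 4/20 = 0.2 grade.
- Two-sided sign test with all changes favourable: five changes give 2 × 0.5⁵ = 0.0625, and six give 2 × 0.5⁶ = 0.031. Six one-sided misgradings would therefore be enough to fall below 0.05 with no true change.

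**Allowing for random rating error (assumed inputs).** Suppose there is no true change, that a fraction q of subjects is misgraded one step in each direction, and that expectation adds a fraction b graded as improved. With u improved and w worsened out of 20,

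P(u, w) = 20! / [u! w! (20−u−w)!] × (q+b)^u × q^w × (1−2q−b)^(20−u−w).

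Summing over every outcome for which the exact two-sided sign test gives p ≤ 0.05:

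| Added shift b | q = 5% | q = 10% | q = 15% |
|---|---|---|---|
| 0 | 0.0% | 0.5% | 1.3% |
| 10% | 3.2% | 4.6% | 5.0% |
| 20% | 19.6% | 17.4% | 15.1% |
| 30% | 45.5% | 36.7% | 30.6% |

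The row b = 0 describes fully effective masking. Partial masking would fall between that row and the others. The sign test is chosen for illustration.

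**Workload of a masked reading.** 20 subjects × 2 time points = 40 photograph sets, and 40 × 2 scales = 80 grades. The FIQ exercise already planned is 200 evaluators × 10 photographs = 2,000 questionnaires.

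**The case against.** The strongest reply is that this is a declared open-label post-market study which masks its raters for the FIQ, the comparison that Section 10.1 uses to establish primary efficacy. OCSS and POLSS are secondary, Sections 10.2.3 and 10.2.4 say improvement rests on them only in part, and no sample size or success rule depends on them. That stands, and it limits the weight of the point.

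The size of the bias is also not in the documents. A reader might infer from the figures above that the improvement will be inflated by 0.2 grade, or that a false positive is likely. The documents do not support this: the counts and the test are assumptions, and nothing in the plan says how far a rater's grade drifts with expectation. The eligibility criteria also admit subjects with no perioral lines. They cannot be graded as improved on POLSS, so fewer than 20 may be open to any shift.

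A reader might also infer that masked photographs would remove the bias and should replace the live grades. That goes too far:

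- The masked reader would be the same PI, who has met all 20 subjects and may recognise them. Fuller lips may reveal the post-treatment set.
- Appendix I specifies full-face views at 1.5 m and no perioral close-up. OCSS and POLSS turn on shallow, barely visible lines, and the documents do not say whether these views show them. Noisier grades could hide real change.
- The photographic baseline is Visit 1, while the live baseline is Visit 2.

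These points argue against making photographs the sole basis for improvement. They do not argue against reporting a masked reading beside the live one.

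**Conclusion.** The point holds as a risk of expectation bias, directed towards improvement, in the before/after change on two secondary endpoints. It rests on three facts in the documents: live grading by a PI who knows the visit, the same PI judging OCR, and no untreated comparison. The size cannot be estimated from the documents, and the documents do not show that bias will occur. The primary FIQ comparison is not affected. The point is worth acting on because a partial safeguard can be built from photographs already scheduled at both time points, in a study that already organises masked photograph rating.

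Masking addresses rater expectation only. It does not supply a control group. It also cannot be applied in this way to PI-GAIS, which by its wording compares with the appearance before treatment.

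**What to change.** Add to Sections 10.2.3 and 10.2.4, with a line in Section 12.4:

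1. After the last subject's last visit, the PI also grades OCSS and POLSS from the Visit 1 and final-visit (Visit 3 or Visit 4) at-rest photographs of all 20 subjects. The sets are read one at a time in random order, with subject code, date and visit hidden.
2. The live grades stay. Report the change on masked grades beside the change on live grades.
3. Describe improvement as free of evident rater expectation only where the two agree, and state beforehand what counts as agreement. Disagreement is not proof of bias, since photographic resolution and the different baseline visit could also cause it.
4. Reconcile the visit labels. Sections 10.2.3 and 10.2.4 place the baseline grade at Visit 1, whereas Section 9.2 and Appendix A place it at Visit 2. They also place every final grade at Visit 4, whereas Section 9.3 has subjects without a touch-up graded at Visit 3.

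Cost: protocol wording, coding of 40 photograph sets, and an estimated one or two hours of PI time for 80 grades. The documents give no costs, so this is a judgement from workload. No extra reader, visit or procedure is needed. The report should state the limits: masking may be partial, fine lines may be harder to grade on these views, and the two baselines come from different visits.
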